7. SELECTION OF PATIENTS

7.1. Study Population

All patients who meet diagnostic criteria in each database between 01 Jun 2015 and 31 Dec 2021 and who meet the eligibility criteria will be considered for these studies.

All diagnosis, treatment, laboratory, and procedure codes used to identify patients and define study variables are listed in Appendix A.

The treatment group will be patients with PBC with a history of inadequate response or intolerance to UDCA who initiated OCA in the study window. The control group will be PBC patients with a history of inadequate response or intolerance to UDCA who were eligible but were not treated with OCA (or off-label fibrates) in the study window. The decision to treat a patient with OCA or UDCA is at the discretion of the treating physician and has been made independent from inclusion in each of the databases.

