7.3. Exclusion Criteria

A patient who meets **any** of the following criteria for a given index date is not eligible for inclusion:

- History or presence of other concomitant liver diseases before the index date (inclusive), including:
 - Acute or chronic hepatitis C virus infection
 - Acute or chronic hepatitis B infection

- Primary sclerosing cholangitis
- Active alcoholic liver disease
- Hepatocellular carcinoma
- Hepatorenal syndrome
- Hepatopulmonary syndrome
- Portopulmonary syndrome
- NASH
- History of non-skin malignancy or melanoma before the index date (inclusive)
- History of HIV before the index date (inclusive)
- Medical conditions that may cause non-hepatic increases in ALP:
 - Paget's disease during the 12-month period before the index date (inclusive)
 - Fractures within 3 months before the index date (inclusive)
- Patients with laboratory values indicative of hepatic decompensation or significant hepatobiliary injury before the index date (inclusive):
 - TB >3 mg/dL
 - ALP >10x ULN
 - ALT and/or AST >10x ULN
- History of liver transplant before the index date (inclusive)
- Evidence of OCA, fenofibrate, or bezafibrate use before the index date (inclusive)
- History or presence of any of the following hepatic decompensating events before the index date (inclusive):
 - Variceal bleeding
 - Ascites
 - Hepatic hydrothorax
 - Spontaneous bacterial peritonitis
 - Hepatic encephalopathy

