 - Komodo Health: The Komodo Health data has been linked to the US National Death Index (NDI), and mortality will be recorded as date of death as recorded in the Index
 - Global PBC registry: Death and date of death are reported by the physician via electronic Case Report Form (eCRF) and recorded through the CASTOR trial platform
- Liver transplantation
 - Komodo Health: The Komodo Health data will be linked to the OPTN database to ascertain whether a patient has received a liver transplant and the date of transplant.
 - Global PBC registry: Liver transplant and date of transplant are reported by the physician via eCRF and recorded through the CASTOR trial platform.
- Hospitalization for hepatic decompensation
 - Komodo Health: Hospitalization for hepatic decompensation will be assessed by any hospital admission claim with the following International Classification of Diseases (ICD)-10 codes (in any position) for decompensating events
 - Variceal bleed: ICD-10: I85.01, I85.11, I86.4 and ICD-9: 456.1, 456.21, 456.8
 - Ascites: ICD-10: K70.11, K70.31, K71.51, R18.0, R18.8, J94.8, K65.2 and ICD-9: 567.23, 571.2, 789.51,789.59, 511.8, 567.23

- Hepatic encephalopathy: ICD-10: B15.0, B16.0, B16.2, B17.11, B19.0, B19.11, B19.21, K70.41, K72.11, K72.90, K72.91 and ICD-9: 572.2, 070.0, 070.20, 070.41, 070.6, 070.71; or utilization of lactulose and/or rifaximin.
- Global PBC registry: Hospitalization for hepatic decompensation and date of hospitalization are reported by the physician via eCRF and recorded through the CASTOR trial platform

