12.4.3. Komodo Health Hospitalization for Hepatic Decompensation

The primary endpoint is a composite of all-cause death, liver transplant, and hospitalization for hepatic decompensation. The primary source for hospitalization for hepatic decompensation will be Komodo Health claims. The definition will include inpatient admission ICD-10 codes that appear in any position, and includes:

- Variceal bleed: ICD-10: I85.01, I85.11, I86.4 and ICD-9: 456.1, 456.21, 456.8
- Ascites: ICD-10: K70.11, K70.31, K71.51, R18.0, R18.8, J94.8, K65.2 and ICD-9: 567.23, 571.2, 789.51,789.59, 511.8, 567.23
- Hepatic encephalopathy: ICD-10: B15.0, B16.0, B16.2, B17.11, B19.0, B19.11, B19.21, K70.41, K72.11, K72.90, K72.91 and ICD-9: 572.2, 070.0, 070.20, 070.41, 070.6, 070.71; or utilization of lactulose and/or rifaximin

As ICD-10 codes are standard across the US healthcare industry, there is no need for further harmonization across contributing health plans.

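### In the Komodo study, lactulose or rifaximin use can satisfy the encephalopathy part of the primary endpoint with no stated need for an admission, a diagnosis or new use

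*Combined protocol and SAP*

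**What the plan says.** For Komodo, Section 8.1 introduces the decompensation component with "Hospitalization for hepatic decompensation will be assessed by any hospital admission claim with the following International Classification of Diseases (ICD)-10 codes (in any position". The variceal bleed and ascites bullets are code lists only. The encephalopathy bullet is a code list that ends "or utilization of lactulose and/or rifaximin". Section 12.4.3 repeats the clause; its lead-in is "The definition will include inpatient admission ICD-10 codes that appear in any position, and includes", and the word inpatient there attaches to the diagnosis codes.

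For the registry, Section 8.1 says "Hospitalization for hepatic decompensation and date of hospitalization are reported by the physician via eCRF" and gives no drug criterion.

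On entry, Section 7.3 excludes "History or presence of any of the following hepatic decompensating events before the index date (inclusive", with encephalopathy in the list that follows. It also names drugs whose earlier use excludes: "Evidence of OCA, fenofibrate, or bezafibrate use before the index date (inclusive". Lactulose and rifaximin are not named. Neither drug is among the weighting covariates in Section 10.1.1. Section 10.9 plans a bias analysis for unmeasured confounding, and the Synopsis adds a check of the claims-based PBC definition. Neither analysis removes the drug clause.

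**The concern.** The component is named as a hospitalisation throughout, and Section 8.1 explains that ascites was recast as a hospitalisation so that the decompensating events would be measured consistently. A drug route with no conditions works against that aim, because a prescription is neither an admission nor a diagnosis.

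Two kinds of misclassified event could enter the Komodo composite and its decompensation component. The first is drug use with no admission. The second is continuing use that began before index and is counted after it. If a patient's encephalopathy history is read from diagnoses alone, a drug-only event would not bar later control indices, so one patient could supply several such events. The patient-level bootstrap in Section 10.5 would account for the correlation between those events but not for the misclassification.

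At stake are the primary hazard ratio in 747-405 and its power. A difference between the two studies on this component could also come from the definition and not from the patients.

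**Working it through.** **Text side by side**

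| Element | Komodo | Registry |
|---|---|---|
| Encephalopathy event | Admission claim with a listed code, or use of either drug | Physician-reported hospitalisation |
| Admission required on the drug route | Not stated | No drug route stated |
| Encephalopathy diagnosis required on the drug route | Not stated | No drug route stated |
| New use required | Not stated | No drug route stated |
| Prior use of these drugs excluded (7.3) | Not named | Not named |

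**Reproducing the plan's power figure.** Inputs from Section 10.4: 395 OCA patients and 5916 controls in Komodo, alpha 0.05 (two-sided per Section 10.3.1), HR 0.5, variance inflation 2.0, stated threshold above 9% events.

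- N = 395 + 5916 = 6311; OCA share p = 395/6311 = 0.0626; p(1−p) = 0.0587.
- Effective events D = 6311 × 0.09 / 2.0 = 284.
- Power = Φ(√(D·p(1−p)) × |ln HR| − 1.96) = Φ(4.08 × 0.693 − 1.96) = Φ(0.87) = 80.8%.

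The rate giving 80% power is 8.8%, which agrees with the stated 9%. The other thresholds come out at 6.6% for Komodo with inflation 1.5 (stated 6%), and at 8.2% and 11.0% for the registry (stated 8% and 11%). The formula is close enough to size the issue.

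**Equal null drug-only events.** The documents give no rate, so this is an assumption. Let f be the share of control events that are drug-only, unaffected by OCA and equally frequent in both groups. Then observed HR = 0.5(1−f) + f. The 5% to 15% event rates in Section 10.4 may or may not include such events, so power is given both ways (Komodo, inflation 2.0).

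| f | Observed HR | Power, total events held at 9% | Power, added to a true 9% |
|---|---|---|---|
| 0 | 0.50 | 80.8% | 80.8% |
| 10% | 0.55 | 68.5% | 73.0% |
| 20% | 0.60 | 55.0% | 64.5% |
| 30% | 0.65 | 42.0% | 55.6% |
| 50% | 0.75 | 21.6% | 38.2% |

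The same dilution in rates, with a true control rate e and a drug-only rate r in both groups, is (0.5e + r)/(e + r). At e = 6% it gives 0.57, 0.67 and 0.73 for r = 1%, 3% and 5%. At e = 10% it gives 0.55, 0.62 and 0.67.

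**Unequal drug-only events.** Assume a true HR of 1 and a true rate of 6% in each group. With drug-only events of 3% in controls and 1% in OCA, the ratio is (6+1)/(6+3) = 0.78. Reversed, it is (6+3)/(6+1) = 1.29. The direction depends on a difference that the documents do not report.

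**The case against.** The best defence is context. The lead-in in Section 8.1 concerns hospital admission claims, and the component is called a hospitalisation everywhere, so the drug clause may only be a second way to recognise encephalopathy within an admission. That reading is available, and the text does not establish that every outpatient prescription was meant to count. But the lead-in refers to codes, the drug clause is joined by an or, and no setting is stated. The narrower reading also leaves the continuing user who is admitted for something else.

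A reader might infer from Appendix A, which has no entry for either drug, that prior users are certainly ignored at entry. That does not follow: the appendix contains no drug codes at all, not even for OCA or the fibrates that Section 7.3 does exclude. Whether drug use counts towards a history of encephalopathy is left unsaid. What stands is that Section 7.3 names other drugs and omits these two.

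A reader might also infer that the studies would match once the clause was gone. They would not. The registry relies on physician report and does not require a listed code, its case report forms are deferred to a supplement (Section 12.1.2), and the studies are analysed separately. The clause adds a difference; it is not the only one.

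Nor do the documents show that the drugs are used for other conditions, that all drug-only events would be false, or that the bias favours OCA. With equal null rates it works against a finding of benefit. Finally, Section 10.11 lets the Clean Room Committee settle variable definitions while blinded. That provides a route to a correction but does not supply the missing rule.

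**Conclusion.** The concern holds as a defect in the Komodo primary event definition. Followed as written, drug use without an admission can be a primary event. On the narrower reading, a continuing user admitted for any reason can still be counted. A prevalent user without an excluding diagnosis could enter and then have an event. This goes beyond missing detail, because the rule as worded departs from the endpoint that the plan names.

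The size of the bias is unknown. The 20% illustration (a true HR of 0.5 read as 0.60, with power falling from 80.8% to 55.0% or 64.5%) rests on an assumed share, on every drug-only event being null, and on equal rates in both groups. Unequal rates can push the estimate either way. The text supports neither the claim that the plan definitely counts all outpatient use nor the claim that the result is biased in favour of OCA.

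**What to change.** Make these changes before the Clean Room Committee releases event data (Section 10.1.2).

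1. In Sections 8.1 and 12.4.3, require a hospital admission claim for every encephalopathy event in the primary analysis. Either delete the drug clause, or limit it to use that is new since index and linked to a qualifying admission, with the link and the event date defined.
2. Apply the same drug rule to baseline history in Section 7.3. If the clause is kept in any analysis, exclude from that analysis indices with use of either drug on or before the index date, and list the drug codes in Appendix A.
3. Prespecify the alternative definition as a sensitivity analysis in Section 10.9: with drug-only events if the primary omits them, without them if the primary keeps them.

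The cost is a few lines of wording and code and one further run. The downside is that some true encephalopathy admissions without a listed code may drop out of the primary count. The documents do not say how many; the sensitivity analysis would help to show whether it matters.

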8.2. Exploratory Outcomes

There will be 3 exploratory evaluations of efficacy, measured as the as-treated:

- Time to first occurrence of all-cause death
- Time to first occurrence of liver transplant
- Time to first occurrence of hospitalization for hepatic decompensation

8.3. Exposure Variable

The exposure variable initiates at the OCA index date. In the Komodo database, OCA exposure will be assessed as date of first filled prescription and quantified as days supply. Discontinuation will be assessed by a gap of >90 days after previous days supply. Treatment exposure will be continued for 90 days after last days supply, after which the OCA-treated patient will be censored. In the Global PBC database, OCA exposure will be from the first physician reported utilization date to discontinuation date, plus 90 days. In this study, exposure can range from 1 to 67 months.

9. ASSESSMENT OF SAFETY

The objective of these replicate observational Real-world Data studies is to evaluate the effective of OCA on hepatic outcomes in patients with PBC. All patients are de-identified in the data sources. These studies are not designed to assess safety, and there are no pre-specified safety analyses. Study outcome variables collected for the 2 cohorts will be presented for analyses as aggregate data groups. The data sources will not be searched for individual patient adverse events; however, if an Investigator or Sponsor identifies adverse events that meet postmarketing reporting requirements during the course of conducting these studies, such events will be reported in accordance with applicable postmarketing reporting requirements.

10. STATISTICAL METHODS

10.1. Analysis Populations and Blinding

10.1.1. Analysis Populations

The statistical analysis of the HEROES PBC studies will follow a nested randomized trial emulation approach (Hernán 2008, Danaei 2013) using a treatment decision design to identify index events (Brookhart 2015). The goal of the study design is to emulate a sequence of hypothetical randomized trials. In each hypothetical trial, patients meeting the inclusion and exclusion criteria who are making the decision whether to initiate OCA-based treatment are

randomized to either continue their existing PBC treatment or switch to an OCA-based treatment. Each randomized patient is then followed until the earliest of the end of follow-up or the time of the study endpoint (death, liver transplant, or hospitalization for hepatic decompensation). Standard survival analysis methods (eg, a Kaplan-Meier estimator of the cumulative incidence function or a Cox proportional hazards model to estimate the hazard ratio) will then be used to estimate the effect of OCA on the study endpoint.

Due to the lack of randomization, non-randomized observational studies will instead be conducted, with the goal of mimicking the hypothetical randomized trial as closely as possible. All patients will be evaluated over time from the start of the study period to identify evidence of inadequate treatment response to UDCA. Each date of inadequate response identified in the data will be considered a treatment decision point, and that date will be considered an index date, with a corresponding record being created in the analytic data for that patient index. Each patient can contribute multiple index dates, and thus patient indices, corresponding to each date they have a treatment decision point, and therefore each patient may contribute person-time to multiple patient index records.

At each treatment decision point, the inclusion and exclusion criteria will be assessed (see Sections 7.2 and 7.3). For patient indices meeting the study criteria, all baseline covariates and treatment variables will be determined. Person-time corresponding to each patient index will be computed relative to the date of the index event. Notably, because prior treatment with OCA is an exclusion criterion, a patient may contribute at most one OCA-treated patient index event, though they can contribute multiple non–OCA-treated patient index events.

After the index date, follow-up will continue until the first of the composite outcome event (all-cause death, liver transplant, or hepatic decompensation), censoring, treatment discontinuation (for patient indices initiating OCA on the index date), OCA initiation (for patient indices not initiating OCA on the index date), or the end of the study period.

Because treatment will not be randomized, it is likely that OCA-treated and non–OCA-treated patient indices will differ on confounding variables, ie, variables that influence both treatment and outcome. Therefore, a simple comparison of outcomes among the OCA-treated versus non–OCA-treated patient indices is likely to yield a biased estimate of the effect of OCA on the study endpoint. To address differences in the covariate distribution between groups, the Sponsor will first conduct descriptive analyses on all baseline variables (demographics, clinical characteristics, and treatment history) for the OCA-treated and non–OCA-treated groups at index. Means, standard deviations, medians, inter-quartile ranges, and minimums and maximums will be provided for continuous variables. Counts and percentages will be provided for categorical variables. Appropriate tests comparing cohorts of interest in the primary and exploratory analyses (eg, t--test, chi-squared test) will be used based on the distribution of the measure.

Next, standardized mortality/morbidity ratio weights will be used to create a "pseudo-population" of non–OCA-treated indices with the same covariate distribution as the OCA-treated patients at the time of OCA initiation (Sato 2003), and unweighted and weighted standardized mean differences (SMDs) will be computed. SMR weights result in an average effect of treatment among the treated. They often make more efficient use of data in a situation with a small treatment group compared with inverse-probability of treatment weights. The SMR weights will be estimated as:

 $w_i^t = \frac{\hat{\pi}_i(1)}{\hat{\pi}_i(A_i)}$, where w_i^t is the weight for patient index *i*, A_i is the observed level of treatment for patient index *i* (A = 1 if the patient index is OCA-treated, 0 otherwise), X_i is the vector of confounders measured at the index time for patient index *i*, and $\pi_i(a) = \Pr(A = a | X_i)$ is the probability that patient index *i* receives treatment level *a* conditional on their covariates.

As the probabilities used to construct the weights are not known, they will be estimated using a logistic regression model. The model will be fit using observed treatment as the outcome and main effect terms for each of the covariates. Covariates (assessed in the pre-index period) will include:

- Age at index date
- Sex
- Most recent liver biochemistry levels (TB, ALP, ALT, AST)
- Most recent platelet counts
- Time (in months) since UDCA failure
- Clinical evidence of portal hypertension (platelets <150,000 and/or non-bleeding varices)
- Cirrhosis
 - Komodo Health: cirrhosis diagnosis with liver imaging and/or biopsy within 6 months before diagnosis
 - Global PBC registry: biopsy stage 4, transient elastography ≥16.9 kPa, radiological evidence (nodular liver or enlargement of portal vein with splenomegaly), clinical features of portal hypertension defined as platelet count <140 000/mm³ with persistent decrease in serum albumin; or, TB >2x ULN, or prothrombin time/INR > ULN (not due to antithrombotic use)
- Most recent Charlson Comorbidity Index Score (Glasheen 2019)
- Insurance type at the index date (Komodo Health only: commercial, Medicare, Medicaid, dual eligible, other)

All diagnosis, procedure and laboratory codes used to define the control variables are listed in Appendix A.

Once the weights are constructed, a table of weighted SMDs between the groups will be constructed to assess balance. An absolute SMD of greater than 0.1 will indicate potentially problematic residual imbalance for the particular covariate. In the case that either the model-fitting algorithm fails to converge, or residual imbalance exists after weighting, the study team will attempt to reduce model complexity or reduce imbalances by implementing one or more of the following actions:

- Adding/removing interaction terms (1st order or higher)
- Using a spline for continuous variables
- Shrinking all coefficients in the model using a penalty

To protect the integrity of the research results, all decisions about updating the analysis will be made by the Investigators without knowledge of how those decisions might affect the outcome (Clean Room Committee [CRC], see Section 10.11). Each decision for a set of actions will be tracked in a study log along with the results presented to the analysis team to inform the action. The final weights will be used for the main analysis. Results for each stage of the developed weights will be documented and presented as supplementary material (and decisions will be recorded in the study log).

Under the identification conditions of causal consistency (Cole 2009, VanderWeele 2009, Pearl 2010), (partial) conditional exchangeability (Greenland 1986, Sarvet 2020), and positivity (Westreich 2010, Petersen 2012), the pseudo-population resulting from weighting the person-indices will emulate the data (at baseline) of the aforementioned hypothetical randomized trial.

10.1.2. Blinding

To ensure that knowledge of outcomes does not influence group creation, all persons involved in the studies will be kept blind to outcomes (death, liver transplant, hospitalization for decompensation) until after the analytic groups are created and the SMR weights are finalized. The event file will be kept separate from the primary data containing patient demographic, medical history, treatment, and laboratory data and will not be accessible to study personnel. Once the OCA-treated and non–OCA-treated datasets are created and approved by the CRC, the CRC will notify non–study-affiliated designees at each site that the event data can now be accessed in order to perform the effect size analysis and statistical testing.

Because treatment non-adherence and loss to follow-up may not occur completely at random, those who remain uncensored may differ from the overall study population on key prognostic factors. To address these differences, the Sponsor will include baseline covariates in the Cox model that are potential predictors of both the study outcomes and censoring.

